3.4. Per-Protocol Analysis Set

The per-protocol (PP) analysis set is a subset of the mITT analysis set including only patients who meet the following criteria:

- compliant with study medication (80% to 105%)
- complete the study without any major protocol deviations that may impact efficacy
- centrally read baseline MD-CRS part II total score ≥ 10

Examples of major protocol deviations that may result in patient exclusion from the PP analysis set are given in [Table 1](#).

Table 1: Possible Types of Major Protocol Deviations that May Lead to Exclusion from the Per-Protocol Analysis Set

Type of deviation	Description of Deviation
Informed consent	Missing informed consent
Inclusion/Exclusion	Patient did not meet inclusion/exclusion criteria
Compliance	Overall compliance during the treatment period <80% or >105%
	Overall compliance during the maintenance period <80% or >105%
Study drug	Patient took incorrect dose for more than 7 days
Dosing error	Patient received the incorrect IMP, contrary to the randomization schedule (eg, patient randomized to placebo group and received a supply of TEV-50717).
Restricted/disallowed Concomitant Medication	Patient took a medication that was not permitted during participation in this study
MD-CRS part II total score	Missing centrally-read MD-CRS part II assessment at baseline
	Patient does not have at least 1 post-baseline centrally read MD-CRS part II assessment

Evaluation of exclusion from the PP analysis set will be discussed on a case-by-case basis and documented prior to database lock and unblinding of the study for final analysis.

3.5. Modified Intent-to-Treat Analysis A Set

The modified intent-to-treat A (mITTA) analysis set is a subset of the mITT analysis set including all patients that received at least 1 dose of IMP.

In the mITTA analysis set, treatment will be assigned based on the treatment to which patients were randomized, regardless of which treatment they actually received.

3.6. Modified Intent-to-Treat Analysis B Set

The modified intent-to-treat B (mITTB) analysis set is a subset of the mITT analysis set including all patients that received at least 1 dose of IMP and have centrally-read MD-CRS part II total score ≥ 10 at baseline.

In the mITTB analysis set, treatment will be assigned based on the treatment to which patients were randomized, regardless of which treatment they actually received.

4. GENERAL ISSUES FOR DATA ANALYSIS

4.1. General

Descriptive statistics for continuous variables include number (n), mean, standard deviation (SD), standard error (SE), median, minimum, and maximum. Mean, SD and SE will not be presented if the number of patients in the analysis is less than 5 ($n < 5$).

Descriptive statistics for categorical variables include patient counts and percentages. Missing category will be displayed as appropriate.

The following variables are used as stratification factors for randomization or determination of titration scheme and maximal dose: CYP2D6 impairment status; weight category; age group; region. For the purpose of analysis, the actual baseline values as derived from the Case Report Form (CRF), or from the CRF and the laboratory database in case of CYP2D6 impairment status, will be used in the case of discrepancy between Randomization and Trial Supply Management (RTSM) and CRF data.

4.2. Specification of Baseline Values

Generally, the baseline value is the last observed data before the first dose of IMP, unless otherwise noted. If the baseline assessments occur on the same day as the first dose of IMP, it is assumed that the patients follow study procedure and those baseline assessments will be used. For patients in the ITT population who took no IMP, the baseline value is the last observed data on or prior to the randomization date. Electrocardiogram/Electrocardiography (ECG) data will follow this rule, unless specified otherwise.

MD-CRS part I and II central reading: for specification of baseline values in case of missing centrally-read MD-CRS part I or II at baseline, see Sections 4.3.1 and 4.3.2.

Baseline values for patients withdrawals and re-enter the study will be defined in Section 4.5.

4.3. Handling Withdrawals and Missing Data

For this study design and population, it is unlikely that patients who withdraw from IMP will be willing to attend the remaining scheduled study visits and, in particular, the week 15 visit. Therefore, patients will not be required to return to the clinic at week 15 for efficacy evaluations, and the primary analysis of the primary and key secondary efficacy endpoints will be based on a multiple imputation method for missing data.

For the primary efficacy and key secondary analyses, missing data will be classified as missing at random (MAR) and MNAR. The following cases will be considered as MNAR:

- early terminations related to tolerability
- early terminations related to treatment-related adverse events
- early terminations related to lack of efficacy

The following cases will be considered as MAR:

- intermittent missing data

- early termination for patients who are lost to follow-up
- early termination due to COVID-19

For all other cases, and for cases classified as above, classification as MAR/MNAR will be done/revisited in a blinded manner on a case-by-case basis prior to the IA for futility and prior to database lock for final analysis and will be documented in a dedicated document.

Multiple imputation methods will be used in the primary and secondary efficacy analyses. See Sections 6.2 - 6.3 for details.

Note: imputation of missing baseline values will be performed prior to implementation of multiple imputations in the analysis model.

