1. STUDY OBJECTIVES

1.1. Primary Estimand

The primary estimand is the difference in means between TEV-50717 and placebo in the target patient population for the change from baseline to week 15 in centrally read Movement Disorder-Childhood Rating Scale (MD-CRS) part II total score, regardless of whether or not dose reduction, suspension, or discontinuation occurred, and regardless of treatment-related adverse events.

The primary estimand assesses the effectiveness in the reduction of choreiform movements in patients with dyskinesia in cerebral palsy (DCP) with predominant choreiform movement disorder, focusing on the causal effects attributable to the investigational medicinal product (IMP).

The target patient population for this study is patients with DCP with predominant choreiform movement disorder and severity of DCP represented by the following:

- a. total score of ≥ 10 in centrally read MD-CRS part II items at baseline, and
- b. Clinical Global Impression of Severity (CGI-S) ≥ 4 at baseline.

This population is expected to have the sensitivity to demonstrate clinically meaningful improvement following treatment with TEV-50717.

Due to practical reasons (periodical assessments), it is not possible to obtain a central reading of MD-CRS part II items at the time of the baseline visit prior to randomization; therefore, inclusion of the patient to the study is based on investigator scoring of MD-CRS part II items at baseline.

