Maintenance period (8 weeks): Patients will continue to receive their maintenance dose over the next 8 weeks, although a 1-time dose reduction (to the previous dose level for the remainder of the study) for adverse events is allowed. Patients will return to the clinic at weeks 9, 12, and 15 for assessments of efficacy and safety.

Washout period and follow-up: All patients will discontinue IMP at the week 15 visit and will return 1 week later for the end-of-study (EOS) visit. Patients who complete the study may be eligible to begin participation in the open label safety extension Study TV50717-CNS-30081 at that time. At the week 16 visit, patients may choose to enter Study TV50717-CNS-30081 (on

¹ The titration scheme is presented in Tables 4 and 5 in the study protocol.

that day) or up to 1 week later (2 weeks from the week 15 visit). Patients who complete treatment but choose not to participate in the open-label safety extension Study TV50717-CNS-30081 before week 17 of Study TV50717-CNS-30080 will be contacted for a safety evaluation call occurring 2 weeks after their last dose of IMP.

The study scheme is presented in [Figure 1](#).

At the time of informed consent, the parent/legal guardian will be counseled that, once randomized to treatment, patients are to remain in the study and complete all study procedures unless the choice is made to withdraw consent. Patients who withdraw from the study before completing the 15 week treatment period should have an early termination (ET) visit as soon as possible after the last dose of IMP. All patients who discontinue early will have a follow-up telephone contact for safety evaluation 2 weeks after ET; evaluations will be as described for week 17.

[figure not shown]
Patients who screen fail or terminate early from the study due to emergency circumstances (such as coronavirus disease 2019 [COVID-19]) may be allowed to re-screen/re-enter (respectively) the study at a later date, depending on the circumstances.

Study procedures and assessments with their timing are summarized in Table 3 of the study protocol.

Interim Analysis: When approximately 50 patients have completed the study (including follow-up), an independent Data Monitoring Committee (iDMC) will perform an unblinded non-binding IA for futility based on centrally read MD-CRS part II total score.

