6.2.3. Primary Efficacy Analysis

The primary analysis will be a mixed-model repeated-measures (MMRM) with the change in MD-CRS part II total score as the dependent variable. The model will include fixed effects for treatment group, week (as a categorical variable with 3 levels: weeks 9, 12, and 15), and treatment group by week interaction. The baseline MD-CRS part II total score, age group at baseline (2 levels: 6 to <12 years; 12 through 18 years, inclusive), and region (US; non-US) will be included as covariates. The unstructured covariance matrix will be used in the model. In cases where the model does not converge, the Maximum-Likelihood estimation method will be used instead of the default Restricted Maximum-Likelihood. If the model still does not converge, then a simpler covariance structure with fewer parameters will be used, according to the following order: Heterogeneous Autoregressive (1), Heterogeneous Compound Symmetry, Autoregressive (1), and Compound Symmetry. The Kenward-Roger approximation will be used to estimate denominator degrees of freedom.

Missing data will be classified as MAR and MNAR, as described in Section 4.3. MNAR data will be imputed using the jump-to-reference method, and MAR data will be imputed based on the randomized treatment group. The details are described below:

1. Missing data will be imputed in 2 separate subgroups. The MAR subgroup will contain all patients randomized to a TEV-50717 treatment group without missing data at week 15 or have a MAR missing data mechanism. The MNAR subgroup will contain all patients randomized to placebo as well as patients randomized to receive TEV-50717 with missing data at week 15 with an MNAR missing data mechanism.
2. Data will be imputed for patients with missing data at week 15 using a predictive mean matching multiple imputation method. Multiple imputations will be performed within each subgroup:
 - a. Under a MNAR data assumption, patients in the MNAR subgroup will have their missing data at week 15 imputed as if they behaved like placebo treated patients after dropping out. Only placebo patients with complete data will be included in the imputation model.
 - b. All other patients will have data imputed from a model derived from their assigned treatment group (imputation under MAR assumption).

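### The estimand applies regardless of discontinuation, but by default active patients lost to follow-up are imputed from the TEV-50717 model, a small unstated departure that favours the drug

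*SAP*

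**What the plan says.** SAP Section 1.1 defines the primary effect "regardless of whether or not dose reduction, suspension, or discontinuation occurred, and regardless of treatment-related adverse events". Section 1.2 attaches the same condition to the five secondary estimands.

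On data collection, two sections pull apart. Section 2.1 has families counselled that, once randomised, "patients are to remain in the study and complete all study procedures unless the choice is made to withdraw consent". Section 4.3 says of those who withdraw from IMP that "patients will not be required to return to the clinic at week 15 for efficacy evaluations", on the ground that they are unlikely to be willing, and turns to multiple imputation.

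Section 4.3 sorts missing data into two classes. Early terminations for tolerability, treatment-related adverse events or lack of efficacy are missing not at random (MNAR). The MAR list contains intermittent gaps, "early termination for patients who are lost to follow-up" and "early termination due to COVID-19". For other cases, and for the listed ones too, "classification as MAR/MNAR will be done/revisited in a blinded manner on a case-by-case basis prior to the IA for futility" and again before database lock.

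Under Section 6.2.3, MNAR patients jump to the placebo reference. MAR patients are imputed within their own arm. The active MAR subgroup consists of "all patients randomized to a TEV-50717 treatment group without missing data at week 15 or have a MAR missing data mechanism". Appendix 1 codes the same split.

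**The concern.** If week-15 values are not required after IMP is stopped, the imputation class decides what outcome a discontinued patient receives. For an active patient lost to follow-up, the default class gives the week-15 outcome of comparable patients who stayed in the TEV-50717 arm. That answers what would have happened had the patient continued, whereas the estimand asks for the outcome whether or not the patient continued.

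The lean is one-sided. A missing placebo patient is imputed from placebo under either class, so only the active arm gains. The rule carries over to the five key secondary endpoints, because Section 6.3.1.1 analyses them in the same fashion as the primary. At stake is whether the reported difference estimates the quantity that Sections 1.1 and 1.2 promise.

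**Working it through.** **Inputs from the SAP.** Section 2.4 gives an effect of 2.0 before MNAR dilution, an SD of 3.5, an expected MNAR rate of 10%, and planned arms of 43 and 22. Section 3.2 requires at least one post-baseline central reading for mITT. Section 6.2.3 and Appendix 1 include baseline, week 9 and week 12 scores in both imputation models.

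**Inputs assumed.** The number of active patients lost to follow-up is not given; four of 43 (9%) is used for illustration. The between-visit correlation ρ is not given; 0.5 to 0.8 is used. The effect and SD are taken as equal at weeks 9, 12 and 15.

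**The plan's own figures.** Dilution: 2.0 × (1 − 0.10) = 1.8, as stated. Sample size: placebo n = 1.5 × (1.960 + 1.282)² × 3.5² / 1.8² = 59.6, so 60, or 180 in total against about 185 stated. Power at 124:61 is 0.908 against about 90%. The inputs therefore reproduce. The dilution covers the MNAR share only; every other missing active patient keeps the full effect.

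**Standard error at the reduced size.** 3.5 × √(1/43 + 1/22) = 0.917.

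**Ceiling.** If earlier scores told nothing about week 15, moving one active patient from active-arm to placebo-reference imputation would change the imputed mean by 2.0 and the arm mean by 2.0/43 = 0.047. Four patients give 0.186.

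**With conditioning on observed scores.** A patient lost before any post-baseline reading is not in mITT. Those who are imputed therefore have at least one observed score, and both models use it.

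- Week 9 observed only: the two imputed means differ by 2.0 × (1 − ρ).
- Weeks 9 and 12 observed, equal correlations: each score has coefficient ρ/(1 + ρ), so the difference is 2.0 × (1 − ρ)/(1 + ρ).

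| Case | Change per patient | Four of 43 | In SE |
|---|---|---|---|
| Ceiling (ρ = 0) | 2.00 | 0.186 | 0.20 |
| Week 9 only, ρ = 0.5 | 1.00 | 0.093 | 0.10 |
| Week 9 only, ρ = 0.8 | 0.40 | 0.037 | 0.04 |
| Weeks 9 and 12, ρ = 0.5 | 0.67 | 0.062 | 0.07 |
| Weeks 9 and 12, ρ = 0.8 | 0.22 | 0.021 | 0.02 |

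**Other loss rates.** The ceiling is 0.02 points per 1% of active patients: 0.04 at 2% and 0.20 at 10%. The conditioning factors in the table run from 0.11 to 0.50, which gives about 0.004 to 0.02 at 2% and 0.02 to 0.10 at 10%.

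**The sensitivity analysis.** Section 6.2.4.1.1 shifts TEV-50717 patients who discontinued for any reason by 0 to 2, or up to the estimated effect if that is larger. In Appendix 2, Step 2, the data step writes out weeks 9, 8 and 12. Week 15 is absent, so as coded the analysis does not reach the primary time point.

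**The case against.** Four objections carry weight.

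- The tipping-point analysis already covers loss to follow-up, and the top of its range removes the full planned benefit. This stands as mitigation. It is not the primary analysis, Section 6.2.4.1.1 sets no rule for acting on it, and its code must be corrected first.
- Loss to follow-up as MAR is a default, open to blinded, documented review. That is so, but the SAP gives no criteria for changing a class, and the starting point is the favourable one.
- COVID-19 terminations raise the same mismatch, so stating a hypothetical strategy could settle loss to follow-up as well. That would make the documents consistent. The cases differ, however: a COVID-19 termination has a known external cause and may lead to re-entry under Section 4.5, while the reason for a loss to follow-up is usually unknown and may relate to treatment.
- Section 2.4 itself calls placebo-based imputation conservative, so it is not shown to be unbiased. This also stands: it removes the lean towards the drug and may overcorrect if some benefit persists.

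A reader might infer more than the SAP supports. Off-drug week-15 data are not required, but it does not follow that they are unwanted, given the counselling in Section 2.1. Nor does the SAP establish that a patient lost to follow-up is off drug at week 15: it gives no dispensing schedule, and Section 5.8 allows for bottles that are not returned. It would also be tempting to set the 0.19-point ceiling against the whole 0.2-point MNAR allowance in Section 2.4, but the mITT definition and the conditioning on earlier scores make that size unlikely.

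**Conclusion.** The mismatch is real and its effect is probably small. For active patients lost to follow-up, the default analysis follows a hypothetical strategy that Sections 1.1 and 1.2 do not state, and it leans towards TEV-50717. Four such patients would add roughly 0.02 to 0.09 points (0.02 to 0.10 SE), with a ceiling of 0.19 points (0.20 SE). This rests on an assumed number of losses, an assumed correlation of 0.5 to 0.8, an equal effect and SD across visits, and the placebo reference standing in for the outcome after loss. If some drug benefit persisted after loss, the lean would be smaller still.

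The SAP does not support calling this a bias that could by itself decide the trial. It does support asking that the primary analysis and its estimand agree, because the correction is cheap and the existing safeguards do not make them agree.

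**What to change.** - **Section 4.3:** make active-arm early termination due to loss to follow-up placebo-reference (MNAR) by default for the primary and key secondary analyses. Keep intermittent gaps and COVID-19 terminations as MAR.
- **Sections 1.1 and 1.2:** state that COVID-19 terminations follow a hypothetical strategy.
- **Sections 2.1 and 4.3:** reconcile them so that patients who stop IMP without withdrawing consent are offered the already scheduled week-15 MD-CRS visit, and any such value is used as the week-15 outcome. Section 4.4 should say so, because Table 2 sends early-termination or unscheduled MD-CRS readings after end of treatment to week 16. This step serves patients who can still be reached; it cannot recover those lost.
- **Appendix 2, Step 2:** output week 15.
- **Appendix 1, week-15 step:** the filter reads `misdm='NMAR'`, while the earlier steps use `missdm='MNAR'`. Unless it is corrected, the reclassified patients would not be selected for week-15 imputation.

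The cost is SAP wording, one change of class and two code corrections, with no new procedure. The estimate becomes slightly less favourable. Sections 2.5.1 and 10.1 bar changes to the main analysis after the interim analysis, so this should be settled before it.

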4.3.1. Specification of Baseline Value for Centrally-Read MD-CRS II

- General rule: baseline assessment (central reading)
- If above not available, then Enrollment Adjudication Board (EAB) screening assessment;
- If above not available, then impute from the local reading of baseline using Regression imputation (see details below);
- If above not available, then the average of the centrally-read baseline MD-CRS part II total score across all patients from the ITT analysis set (Section 3.1) with baseline value.

Regression imputation is a single imputation method. Let Y_1 be the local reading of baseline MD-CRS II total score; Y_2 be the centrally-read MD-CRS II. On the observed pairs (Y_1, Y_2) , fit Y_2 based on Y_1 as $\hat{Y}_2 = Y_1\beta + \alpha$ using linear regression. Impute the missing Y_2 values using the predicted value for a given Y_1 .

4.3.2. Specification of Baseline Value for Centrally-Read MD-CRS I

- General rule: baseline assessment (central reading);
- If above not available, then impute from the local reading of baseline using Regression Imputation (see Section 4.3.1 for details);
- If above not available, then the average of the centrally-read baseline MD-CRS part I total score across all patients from the ITT analysis set (Section 3.1) with baseline value.

4.3.3. Specification of Baseline Value For Clinical Global Impression of Severity

If the baseline assessment of the Clinical Global Impression of Severity (CGI-S) is not available, then the average of the baseline CGI-S assessments across all patients from the ITT analysis set (Section 3.1) with baseline value will be used instead. Note that this imputation rule will only be applied for the analysis of the Clinical Global Impression of Improvement (CGI-I).

4.3.4. Specification of Baseline Value for Centrally-Read UHDRS-TMC and TMD

- General rule: baseline assessment (central reading);

- If above not available, then impute from the local reading of baseline using Regression Imputation (see Section 4.3.1 for details);
- If above not available, then the average of the centrally-read baseline value across all patients from the ITT analysis set (Section 3.1) with baseline value.

4.3.5.2. Other Missing Items in Rating Scales

Rules for handling missing items in efficacy and safety rating scales are presented in Section 6.4 (Unified Huntington’s Disease Rating Scale-Total Motor Score (UHDRS-TMS), Unified Huntington’s Disease Rating Scale-Total Maximal Chorea (UHDRS-TMC), Unified Huntington’s Disease Rating Scale-Total Maximal Dystonia (UHDRS-TMD), Pediatric Evaluation Disability Inventory-Computer Adapted Test (PEDI-CAT), Pediatric Quality of Life Inventory (PedsQL) and Patient Global Impression of Improvement (PGI-I)) and Section 8 (Columbia-Suicide Severity Rating Scale [C-SSRS], Child Behavior Checklist [CBCL], Extrapyrimal Symptom Rating Scale [ESRS] and Epworth Sleepiness Scale [ESS]).

Unless otherwise specified, only those observed data from the patients will be used in the statistical analyses, ie, no estimation of missing data.

4.4. Study Days and Visits

Study days will be numbered relative to the baseline visit date. Day 1 is defined as the date of the baseline visit, and the first dose of the IMP will be taken the next morning (day 2). Days will be numbered relative to baseline (ie, ..., -2, -1, 1, 2, ...; day -1 being the day before the baseline visit).

For efficacy and safety by-visit analyses, data collected at post-baseline scheduled visits will be included using their scheduled visit.

Data collected at early termination and unscheduled visits will be included and assigned to a visit window as described below.

Table 2: Visit Windows for Early Termination Visit for Efficacy Assessments

Assessment ^a	Study Day Window	Scheduled Day	Scheduled Visit/Week
MD-CRS	Day 2 - 73	Day 63	Week 9
	Day 74 - 94	Day 84	Week 12
	Day 95 - EOT	Day 105	Week 15
	≥Day after EOT	Day 112	Week 16
CaGI-I, CGI-S, PGI-I	Day 2 - 35	Day 21	Week 3
	Day 36 - 53	Day 49	Week 7
	Day 54 - 73	Day 63	Week 9
	Day 74 - 94	Day 84	Week 12
	Day 95 - EOT	Day 105	Week 15
	≥Day after EOT	Day 112	Week 16
CGI-I	Day 2 - 10	Day 7	Week 1
	Day 11 - 17	Day 14	Week 2
	Day 18 – 24	Day 21	Week 3
	Day 25 - 31	Day 28	Week 4
	Day 32 - 38	Day 35	Week 5
	Day 39 - 45	Day 42	Week 6
	Day 46 - 53	Day 49	Week 7
	Day 54 - 73	Day 63	Week 9
	Day 74 - 94	Day 84	Week 12
	Day 95 - EOT	Day 105	Week 15
	≥Day after EOT	Day 112	Week 16
PEDI-CAT, PedsQL	Day 2 – EOT	Day 105	Week 15

Assessment ^a	Study Day Window	Scheduled Day	Scheduled Visit/Week
UHDRS-TMS, UHDRS-TMC, UHDRS-TMD	Day 2 - 73	Day 63	Week 9
	Day 74 - 94	Day 84	Week 12
	≥Day 95 - EOT	Day 105	Week 15

^a CaGI-I=Caregiver Global Impression of Improvement; CGI-I=Clinical Global Impression of Improvement; CGI-S=Clinical Global Impression of Severity; PGI-I=Patient Global Impression of Improvement; UHDRS-TMS=Unified Huntington’s Disease Rating Scale-Total Motor Score; UHDRS-TMC=Unified Huntington’s Disease Rating Scale-Total Maximal Chorea; UHDRS-TMD=Unified Huntington’s Disease Rating Scale-Total Maximal Dystonia; EOT=end of treatment

Table 3: Visit Windows for Early Termination Visit for Safety Assessments

Assessment ^a	Study Day Window	Scheduled day	Scheduled Visit/Week
Vital signs, Weight, C-SSRS, ESRS, CBCL- Syndrome Scale, ESS	Day 2 - 35	Day 21	Week 3
	Day 36 - 53	Day 49	Week 7
	Day 54 - 74	Day 63	Week 9
	Day 75 - 94	Day 84	Week 12
	Day 95 – EOT	Day 105	Week 15
	≥Day after EOT	Day 112	Week 16
ECG	Day 2 - 35	Day 21	Week 3
	Day 36 - 67	Day 49	Week 7
	Day 68 – EOT	Day 105	Week 15
	≥Day after EOT	Day 112	Week 16
Laboratory tests other than pregnancy and drug screen	Day 2 – EOT	Day 105	Week 15
	≥Day after EOT	Day 112	Week 16
Orthostatic blood pressure, Physical exam, Neurological exam, height, CBCL-full assessment	Day 2 – EOT	Day 105	Week 15

^a CBCL=Child Behavior Checklist (for ages 6-18); C-SSRS=Columbia-Suicide Severity Rating Scale; ECG=electrocardiogram; ESRS=Extrapyramidal Symptom Rating Scale (subscales I and II); ESS =Epworth Sleepiness Scale (for children and adolescents); EOT=end of treatment

After mapping the data to the analysis visits of unscheduled and early termination visits, the following rules will apply unless other handling is specified for a particular analysis:

- If there is a scheduled visit in the analysis window, the last non- missing scheduled visit will be selected.
- If there is no scheduled visit, but early termination visit, early termination visit will be selected.

- If there are no scheduled or early termination visits, the record closest to the planned assessment day will be selected for analysis.
- If there are no scheduled or early termination visits, and 2 records are equidistant from the scheduled day, then the later record will be selected.
- If a patient has no scheduled record or early termination/unscheduled visits in an analysis window, the patient will be considered missing at that visit.

For these analyses performed by time period, eg, adverse events, the following definitions will be used:

- Titration Period - from the first dose of treatment until the day of the week 7 visit. For patients discontinued before the week 7, the Titration Period is until the later of the last dose of treatment and the early termination visit.
- Maintenance Period - from the day after the week 7 visit until the day of the week 15 visit. If a patient enters the Maintenance Period but discontinues treatment early, the Maintenance Period is until the later of the last dose of treatment and the early termination visit.
- Overall Treatment Period - includes the Titration and the Maintenance Periods, if applicable.
- Follow-up Period - from the end of the Overall Treatment Period through the end of the study.

For last assessment, the last available non-missing value will be used. Unscheduled visits that could not be mapped will not be displayed in the safety by-visit summaries, but they will be considered for the endpoint/last assessment visit.

